4.3 Analysis Population Subgroups

The following subgroups will be analyzed separately.

BMI group at enrollment:

- $<30 \text{ kg/m}^2$
- $\geq 30 \text{ kg/m}^2$

Race group:

- White
- Non-white

Parity status at enrollment:

- Parous having given birth 1 or more times
- Nulliparous having never borne children

Age at Enrollment:

- \leq 35 years old
- 36-45 years old

4.4 General Data Presentation Plan

Analyses will be conducted using SAS® software, Version 9.4 or above (SAS Institute Inc, Cary, NC).

Analyses will be conducted using the initial 3-year data to support submission for VeraCept approval, and data will be reanalyzed at the end of the 5-year follow-up. Unless otherwise specified, the table summary for the main study will display columns as follows:

Analysis Population	Table Display Columns				
ITT	Age (years) \leq 35	Age (years) 36-45	Overall		
Safety	Age (years) \leq 35	Age (years) 36-45	Overall		
EP	Age (years) \leq 35				
ECYC	Age (years) \leq 35	Age (years) 36-45	Overall		

Other subgroup analyses (race group, BMI group at enrollment, parity at enrollment) will be conducted for all subjects in the corresponding population without further sub-setting by other subgroup variables.

In general, all efficacy and safety variables will be summarized using descriptive statistics and graphs as appropriate. Continuous variables will be summarized by descriptive statistics (sample size (n), mean, SD, minimum, median, and maximum). Categorical variables will be summarized

in frequency tables (frequencies and percentages). Time to event variables will be summarized by Kaplan-Meier method. Individual data will be presented in subject listings.

Means and medians will be displayed with 1 more decimal place than the collected data, and SDs will have 1 more decimal place than the means and medians. Minimum and maximum will be displayed with the same number of decimal places as the collected data. Percentages will be rounded to 1 decimal place.

No formal statistical testing will be performed on demographic, baseline characteristic, and safety data unless stated otherwise for a specific parameter in the SAP. For efficacy variables, all statistical tests will be conducted at a 2-sided significance level of 5% unless otherwise specified. Where appropriate, point estimates, together with their 95% CIs, will be presented.

Only observed data, with no data imputation, will be used for the efficacy analyses unless otherwise specified. Safety analyses will also be conducted on the observed data. However, for the start date/time of an AE or medication being partially or completely missing, the worst-case scenario will be applied. That is, the AE will be assumed to be treatment emergent, and the medication will be considered concomitant.

4.5 Disposition of Subjects

Disposition of subjects will be summarized for the ITT population.

For the initial 3-year study participation:

A disposition table will report the following:

- The number and percentage of subjects who were enrolled, completed Year 1 (first 13 cycles), and discontinued the study during Year 1 with reason for discontinuation
- The number and percentage of subjects who entered Year 2 (second 13 cycles), completed Year 2, and discontinued the study during Year 2 with reason for discontinuation
- The number and percentage of subjects who entered Year 3 (third 13 cycles), completed Year 3, and discontinued the study during Year 3 with reason for discontinuation
- The number and percentage of subjects who were enrolled, completed 3 years, and discontinued the study during the 3 years with reason for discontinuation
- The number and percentage of subjects in each analysis population

A Kaplan-Meier plot will be used for the number of cycles from the date of successful VeraCept placement to study discontinuation.

- The table summary and Kaplan-Meier figure will be repeated by parity at enrollment
- Table summary will further be repeated for each clinical site

Listings will be generated for the following:

- Subject's membership in each analysis population and reason for exclusion from each analysis population
- Subjects with inclusion/exclusion criteria violations and waivers

Five-year participation:

At the end of the 5-year study, a summary of subject disposition for Year 4 (the fourth 13 cycles) and Year 5 (the fifth 13 cycles), separately, and for 5 years cumulatively will be added to the above 3-year disposition table. Kaplan-Meier plots will be created using 5-year disposition data.

4.6 Protocol Deviations

Number (%) of subjects with protocol deviations will be summarized by category (major/minor) and deviation type for the ITT population. The detail about each protocol deviation will be presented in the protocol deviation listing.

4.7 Baseline Demographics and Characteristics

Baseline demographics will be summarized for the ITT, EP, Safety, and ECYC populations. All other baseline characteristic information will be summarized for the ITT population only.

4.7.1 Baseline Demographics

The following variables collected at Screening/Baseline will be included in the baseline demographics summary table:

- Ethnicity
- Race
- Age (years) at enrollment
- Height (cm) at enrollment
- Weight (kg) at enrollment
- BMI (kg/m²) at enrollment
- BMI group ($<30 \text{ kg/m}^2$, $\ge 30 \text{ kg/m}^2$) at enrollment
- Marital status at enrollment
- Parity at enrollment
- Uterine depth

All demographic and baseline characteristics will be presented in data listings.

4.7.2 Medical/Surgical History

Number (%) of subjects reporting Medical /Surgical history will be summarized by Medical Dictionary for Regulatory Activities (MedDRA) primary system organ class (SOC) and preferred term (PT).

An additional summary will be provided for Medical/Surgical history recorded as ongoing. Medical/Surgical History will be presented in a data listing.

4.7.3 Baseline Physical Examination

Physical examination by body system (General appearance, Skin, Head, eyes, ears, nose and throat, Thyroid, Lungs, Back, Breasts, Heart, Abdomen, Extremities, Neurological) will be summarized by age group and overall.

4.7.4 Gynecological History

Gynecological history data will be summarized for all questions collected on the case report form (CRF).

All gynecological history will be presented in a data listing.

4.7.5 Menstrual History

Menstrual history data will be summarized for all questions collected on the CRF.

All menstrual history will be presented in a data listing.

4.7.6 Cervical Cytology

Cervical cytology test results will be summarized in table and presented in a data listing.

4.7.7 Prior and Concomitant Medications

Prior and concomitant medications include any medications taken by subjects from 30 days prior to the signing of the informed consent through the end of study participation will be recorded on CRF page and coded using the WHODrug dictionary. The CSR will include the version number of the WHODrug dictionary. Prior medications are defined as those taken by the subject prior to the study drug placement. Concomitant medications are defined as those taken by the subject from the date of the study drug placement to study completion/discontinuation.

In cases where it is not possible to define a medication as prior or concomitant, the medication will be classified as concomitant.

The number (%) of subjects taking prior and concomitant medications will be summarized, separately, by ATC Level 4 and generic term for the ITT population.

All prior and concomitant medications will be presented in a data listing.

4.8 Extent of Exposure

Following parameters will be summarized for the Safety and EP populations, and summarized by parity at enrollment for the Safety and EP populations:

- Number of exposure cycles including partial cycles
- Number of complete exposure cycles
- Number of relevant cycles
- Number of cycles with back-up contraception or no intercourse
- Number of evaluable cycles for Pearl Index Calculation
- Exposure in woman years

- Exposure in woman years calculated from complete cycles
- Exposure in woman years calculated from relevant cycles
- Exposure in woman years calculated from evaluable cycles

4.9 Primary Endpoint Analysis

The primary efficacy endpoint is contraceptive efficacy through 3 years of use and will be analyzed using the Pearl Index with a 95% CI (CI) for women in the EP population.

The Pearl Index is defined as the number of on-treatment pregnancies per 100 women years. On-treatment pregnancy is defined as the estimated conception date being after the insertion date and no more than 7 days after the VeraCept is removed or expelled. One woman year is defined as comprising thirteen 28-day cycles.

Point estimate of Pearl Index:
$$x \times \frac{1300}{E}$$

95% CI: $\left(\frac{1}{2}\chi_{(0.025,2x)}^2 \times \frac{1300}{E}, \frac{1}{2}\chi_{(0.975,2(x+1))}^2 \times \frac{1300}{E}\right)$

where x is the number of on-treatment pregnancies and E is the number of 28-day evaluable exposure cycles and $\chi^2_{(p,df)}$ is the pth quantile of χ^2 -distribution with df degrees of freedom.

Cycles during which no intercourse occurs or backup methods of contraception (including emergency contraception) are used or there is no diary data will be excluded from the primary analysis of the Pearl Index unless the subject had an on-treatment pregnancy in that cycle. If Cycle 1 is evaluable, it will be included in the analysis regardless of the timing of VeraCept relative to the subject's last pre-insertion menses.

x =sum of PREGNANCY

E =number of Evaluable Cycles (NCYCEV)

Pearl Index point estimate and 95% CI will be calculated for Year 1, Year 2, and Year 3, separately, and for 3 years cumulatively.

The analysis will be repeated for the following subgroups

- Race (white, non-white)
- BMI group at enrollment
- Age group at enrollment
- Parity at enrollment

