20.1 Analysis Populations

The following analysis populations will be created:

• Intent to Treat (ITT):

All subjects who underwent the study drug placement procedure, regardless of whether the study drug was successfully placed or not.

• Safety:

ITT subjects who had the study drug successfully placed

• Safety Subgroup (36-45 years):

Subjects in the safety population who were between 36 to 45 years of age (inclusive) at enrollment.

• Evaluable for Pregnancy (EP):

ITT subjects who had VeraCept placed successfully and meet requirements 1, 2 and 3 below. Subjects must also meet either requirement 4 or requirement 5 to be part of the EP study population:

- 1. Be post-menarcheal up to 35 years of age (inclusive) at enrollment
- 2. Have at least one report of pregnancy status after being enrolled
- 3. Do not have pre-treatment pregnancy, which is defined as the estimated conception date being before the insertion date.

AND

4. Have at least 1 cycle of e-diary with intercourse and without any backup contraception or emergency contraception (EC)

OR

5. Have an on-treatment pregnancy, which is defined as the estimated conception date being on or after the insertion date and no more than 7 days after the VeraCept is removed or expelled.

Subjects with major protocol violations that are deemed to have had a material impact on the primary efficacy assessment will be excluded from EP analysis population. Exclusions based on major protocol deviations will be reviewed and approved by Sebela and its designee.

• Evaluable for Cycle Control (ECYC):

ITT VeraCept subjects with at least one cycle for which:

1. A pregnancy did not occur;

AND

2. There was an assessment of bleeding reported by the subject.

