4.1.5 Exposure Periods

The first exposure cycle starts on Day 1 of successful study drug insertion. A full exposure cycle is comprised of 28 days. One woman-year comprises thirteen 28-day cycles. The following exposure periods are defined for analysis in terms of planned study days and study cycles to facilitate the efficacy and certain safety analyses.

Exposure Period	Study Day of Period Start (PSTDY)	Study Day of Period End (PENDY)
Year 1 (Cycle 1- Cycle 13)	1	364
Year 2 (Cycle 14-Cycle 26)	365	728
Year 3 (Cycle 27-Cycle 39)	729	1092
Year 4 (Cycle 40-Cycle 52)	1093	1456
Year 5 (Cycle 53-Cycle 65)	1457	1820
First 2 Years (Cycle 1-Cycle 26)	1	728
First 3 Years (Cycle 1-Cycle 39)	1	1092
First 4 Years (Cycle 1-Cycle 52)	1	1456
5 Years (Cycle 1-Cycle 65)	1	1820

Type of Events and Study Day During an Exposure Period

ЕТҮРЕ	Event	Study Day of Event (EVTDY)		
A	Expulsion	Study Day of Expulsion date		
В	Expulsion followed by conception within 7 days	Study Day of Expulsion date		
С	Removal	Study Day of Removal date		
D	Removal followed by conception within 7 days	Study Day of Removal date		
Е	Pregnancy before expulsion	Study Day of Conception date		
F	Pregnancy before removal	Study Day of Conception date		
Н	Lost to follow-up without pregnancy, expulsion or removal	Study Day of Last Date Device in Situ.		
I	Complete period without pregnancy, expulsion or removal	Study Day of Period End Date		

Note: Removal due to partial expulsion will be treated as expulsion

Exposure Duration in Days (EXDUR):

if EVTDY-PSTDY>0 then EXDUR = min(EVTDY-PSTDY+1, PENDY-PSTDY+1); else EXDUR=.;

Exposure Duration in Cycles (NCYCF) = EXDUR/28

Number of Completed Cycles (NCYCC) = INT(NCYCF)

Number Relevant Cycles (NCYCR)

- =NCYCC+1 if last partial cycle is >=23 days
- =NCYCC+1 if last partial cycle ETYPE is B or D or E or F
- =NCYCC, otherwise.

Number of Cycles with back-up contraceptives (including emergency contraception) or no intercourse within the period or there is no diary data (NCYCEXCL):

Exclude from NCYCEXCL the cycle in which the subject had an on-treatment pregnancy (ETYPE is B, D, E, F).

Back-up contraceptives or intercourse history are recorded in subject's diary.

If there are missing values then they will be handled as follows:

Missing back-up contraceptive diary entries will be treated as no back-up contraceptive use.

Missing intercourse diary will be treated as no intercourse.

Number of Evaluable Cycles (NCYCEV) = NCYCR-NCYCEXCL

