4.1.6 Pearl Index

Pearl Index is defined as the number of on-treatment pregnancies per 100 women years. On-treatment pregnancy is defined as the estimated conception date being on or after the insertion date (must be a successful insertion) and no more than 7 days after the study drug is removed or expelled. One women year is defined as comprising thirteen 28-day cycles.

Point estimate of Pearl Index: $x \times \frac{1300}{E}$

where x is the number of on-treatment pregnancies and E is the number of 28-day evaluable exposure cycles

Cycles during which no intercourse occurs or backup methods of contraception (including emergency contraception) are used or there is no diary data will be excluded from the primary analysis of the Pearl Index unless the subject had an on-treatment pregnancy in that cycle. If Cycle 1 is evaluable, it will be included in the analysis regardless of the timing of study drug placement relative to the subject's last pre-insertion menses.

If ETYPE is B or D or E or F, then PREGNANCY = 1; else PREGNANCY = 0

x = sum of PREGNANCY

E = Number of Evaluable Cycles (NCYCEV)

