4.2 Analysis Populations

4.2.1 Analysis Populations

• ITT

All subjects who underwent the study drug placement procedure, regardless of whether the study drug was successfully placed or not.

• Safety:

ITT subjects who had the study drug successfully placed

• Safety Subgroup (36-45 years):

Subjects in the Safety population who were between 36 to 45 years of age (inclusive) at enrollment.

• Evaluable for Pregnancy (EP):

ITT subjects who had VeraCept placed successfully and meet requirements 1, 2 and 3 as follows. Subjects must also meet either requirement 4 or requirement 5 to be part of the EP study population:

- 1. Be post-menarcheal up to 35 years of age (inclusive) at enrollment
- 2. Have at least one report of pregnancy status after being enrolled
- 3. Do not have pre-treatment pregnancy, which is defined as the estimated conception date being before the insertion date.

AND

4. Have at least 1 cycle of e-diary with intercourse and without any backup contraception or emergency contraception

OR

5. Have an on-treatment pregnancy, which is defined as the estimated conception date being on or after the insertion date and no more than 7 days after the VeraCept is removed or expelled.

Subjects with major protocol violations that are deemed to have had a material impact on the primary efficacy assessment will be excluded from EP analysis population. Exclusions based on major protocol deviations will be reviewed and approved by the Sebela and its designee.

• Evaluable for Cycle Control (ECYC):

ITT subjects with at least one cycle for which:

1. A pregnancy did not occur;

AND

2. There was an assessment of bleeding reported by the subject.

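### Three boundary rules in SAP 4.9 and 4.1.5 are wrong as written and need a minor correction; no material effect on the primary Pearl Index is shown

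*SAP*

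**What the plan says.** **Insertion-day conception.** SAP 4.9 says: "On-treatment pregnancy is defined as the estimated conception date being after the insertion date". A few lines later the numerator is given as "x =sum of PREGNANCY". That flag is defined in SAP 4.1.6: "If ETYPE is B or D or E or F, then PREGNANCY = 1; else PREGNANCY = 0". It depends on event type only. The text above it in 4.1.6 reads "On-treatment pregnancy is defined as the estimated conception date being on or after the insertion date (must be a successful insertion", and criterion 5 of the EP population in SAP 4.2.1 reads "Have an on-treatment pregnancy, which is defined as the estimated conception date being on or after the insertion date". Protocol 20.1 agrees: "estimated conception date being on or after the insertion date and no more than 7 days after the VeraCept is removed or expelled".

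**First-day event.** SAP 4.1.5 computes exposure as "if EVTDY-PSTDY>0 then EXDUR = min(EVTDY-PSTDY+1, PENDY-PSTDY+1); else EXDUR", with the last value set to missing. The rule for relevant cycles (NCYCR) then gives any pregnancy cycle a full cycle: "NCYCC+1 if last partial cycle ETYPE is B or D or E or F". SAP 4.1.2 makes the date of successful insertion Day 1 of Cycle 1.

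**Excluded cycles.** SAP 4.1.5 defines one count, NCYCEXCL, for cycles with backup contraception, no intercourse or no diary data. It is subtracted from NCYCR to give evaluable cycles (NCYCEV, the Pearl Index denominator), and from CYCLEN to give the compressed Kaplan-Meier time (CYCLENAC). NCYCR omits a final part-cycle under 23 days unless it ends in pregnancy. CYCLEN rounds up, so it always counts that part-cycle.

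**The concern.** The section that defines the primary endpoint disagrees with its own formula on one kind of event. A program built on the sentence drops an insertion-day conception; one built on the flag counts it. Dropping it favours the product.

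The exposure rule appears meant to blank events before a period starts, but its strict inequality also blanks the first day. A Day 1 pregnancy would then be in the numerator with no cycle in E and no Kaplan-Meier time, although SAP 4.10.1 expects the two analyses to be comparable. A Day 1 expulsion or removal would have no time in the expulsion and continuation analyses, which also use CYCLEN.

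For the third rule, if the short final part-cycle is itself non-evaluable, no single value of NCYCEXCL is right for both subtractions. Independent programmers could get different results without either departing from the SAP.

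**Working it through.** **The plan's own figure.** SAP 3.7 expects 577 evaluable woman-years in Year 3, with the upper 95% bound no more than 1 above the index. Under the exact interval in SAP 4.9, the woman-years needed are 100 × (χ²(0.975, 2(x+1))/2 − x). At x = 3: 100 × (17.535/2 − 3) = 576.7, which rounds up to 577. The documents do not state x = 3; it is inferred because it returns 577.

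**1. Insertion-day conception.** One pregnancy is worth 100 divided by the evaluable woman-years. The evaluable share is not in the documents; 80% is an assumption.

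| Period | Assumed evaluable woman-years | Per pregnancy |
|---|---|---|
| Year 1, all cycles evaluable | 17,000 × 1,480/1,605 ÷ 13 = 1,206 | 0.083 |
| Year 1, 80% evaluable | 1,206 × 0.80 = 965 | 0.104 |
| 3 years, constant attrition, 80% evaluable | 2,965 × 0.80 = 2,372 | 0.042 |
| 3 years, Year 3 exposure repeated | 3 × 577 = 1,731 | 0.058 |

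The 17,000, 1,480, 1,605, 620 and 577 come from SAP 3.7. Constant attrition from 1,480 to 620 women gives a rate of −ln(620/1,480)/3 = 0.290 per year and (1,480 − 620)/0.290 = 2,965 woman-years. With every cycle evaluable, the three-year figure would be 100/2,965 = 0.034. An insertion-day conception affects only Year 1 and cumulative results.

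**2. First-day event.** The 4.1.5 rules applied to boundary cases:

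| Event | As printed (>0) | With >=0 |
|---|---|---|
| Pregnancy, Day 1, 3-year period | all missing | EXDUR 1, NCYCR 1, CYCLEN 1 |
| Pregnancy, Day 2, 3-year period | EXDUR 2, NCYCR 1, CYCLEN 1 | same |
| Removal, Day 1, 3-year period | all missing | EXDUR 1, NCYCR 0, CYCLEN 1 |
| Pregnancy, Day 365, Year 2 period | all missing | EXDUR 1, NCYCR 1, CYCLEN 1 |
| Pregnancy, Day 365, 3-year period | EXDUR 365, NCYCR 14, CYCLEN 14 | same |

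One missing cycle barely moves the index. With x = 3 and E = 577 × 13 = 7,501, it goes from 3,900/7,501 = 0.5199 to 3,900/7,500 = 0.5200. One event lost from a Kaplan-Meier analysis is worth about 100/1,480 = 0.07 percentage points for pregnancy (EP, at most 1,480 women) and about 100/1,605 = 0.06 for expulsion or continuation (Safety, at most 1,605).

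**3. Excluded cycles.** Take a removal on Day 66, with two full evaluable cycles and a non-evaluable final part-cycle. EXDUR = 66 and NCYCF = 66/28 = 2.36. The part-cycle is 66 − 56 = 10 days, so NCYCR = 2 and CYCLEN = 3.

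| NCYCEXCL | NCYCEV = 2 − NCYCEXCL | CYCLENAC = 3 − NCYCEXCL |
|---|---|---|
| 0 (part-cycle not counted) | 2, right | 3, one too many |
| 1 (part-cycle counted) | 1, one too few | 2, right |

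On the natural reading, exclusions are counted only among relevant cycles (first row). The Pearl Index is then correct, and the Kaplan-Meier analysis keeps at risk a cycle that SAP 4.10.1 excludes. To size this, exits were simulated under the constant attrition above, with an assumed 0.73 pregnancies per 100 evaluable woman-years (the Phase 2 three-year value in protocol 1.1.3) and 20% of full cycles assumed excluded. Over an assumed 10% to 90% of short part-cycles being non-evaluable, the Year 1 percentage reads 0.002 to 0.014 points too low, against a correct value of 0.7275. At one decimal, both versions print 0.7.

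**The case against.** The strongest reply is that the documents already settle the first point. SAP 4.9 names the variable to be summed, and three other places include the insertion day, so a program following the formula counts the event. That stands. The stray sentence bites only if a programmer ignores the flag and an estimated conception date also falls exactly on insertion day, despite the pregnancy checks at entry. The documents give no expected number of such cases.

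On the second point, the inequality could be a character lost from the PDF. SAP 4.1.2 prints only > and < with no rule for equal dates, although its +1 formula would return Day 1; that suggests a lost symbol there. SAP 4.1.5 preserves >=23 a few lines below the exposure rule, so a loss is less likely in that line, but it cannot be excluded.

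On the third, a reader might infer more than the text supports:

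- **An exclusion share.** It is tempting to divide 577 by modelled Year 3 exposure and call the shortfall the planned share of non-evaluable cycles. The documents do not support this. The figure is reproduced as a precision requirement, the modelled exposure is not a plan figure, and a share for whole cycles need not apply to part-cycles.
- **A damaged primary denominator.** If NCYCEXCL also counted part-cycles absent from NCYCR, E would be too small and a single-year count could go negative. The SAP does not call for that reading, and its size would depend on a share that is not given.

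**Conclusion.** All three rules are wrong as written at a boundary. This is a correction of the lowest priority. The first affects results only if a program follows the sentence instead of the flag, and would then favour the product. The second holds as printed, subject to a check of the source file; its main consequence is a missing Kaplan-Meier time, not a changed Pearl Index. The third leaves the Pearl Index intact on the natural reading, and its Kaplan-Meier effect, slightly in favour of the product, is below the one-decimal reporting in SAP 4.4.

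A reader might conclude that the primary efficacy result is biased. The documents do not support that: the named numerator is right, and nothing suggests that first-day events will be more than rare. The sizes given rest on assumed exposure, attrition and evaluable shares.

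**What to change.** - **SAP 4.9:** include the insertion day, so that the sentence matches 4.1.6, 4.2.1 and the protocol.
- **SAP 4.1.5, exposure rule:** use EVTDY-PSTDY>=0. Check this line and the study-day rule in 4.1.2 against the source file.
- **SAP 4.1.5, NCYCEV:** count exclusions only among cycles included in NCYCR.
- **SAP 4.1.5, CYCLENAC:** use a separate exclusion count over all cycles up to CYCLEN.

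The cost is four short edits and the matching code lines, with no new data. They can go into the SAP that protocol section 20 says will be finalized before database lock; the present one is written to protocol version 3.0. Any existing program should be checked for the same four points.

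The last edit does not make Kaplan-Meier and Pearl Index exposure identical. Short final part-cycles that are evaluable will still count in CYCLEN and not in NCYCR.
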